### 8.2 Prior and Concomitant Medications and Therapies

Prior and concomitant medications will be coded using the World Health Organization (WHO) Drug Dictionary (WhoDrugDDEB3 – 201909). Prior medications and therapies will be defined as medication taken prior to Day 0. Concomitant medications and therapies will be defined as medication taken after first dosing.

For the mITT population, the number and proportion of patients who took prior and concomitant medications will be summarized with WHO Drug Dictionary Preferred Term (PT) by category (laxative, opioid, and others) for each treatment group. If a patient has more than 1 drug that codes to the same PT, the patient will be counted only once for that PT.

The number and proportion of patients who took prior and concomitant therapies will be summarized by the preferred term in each treatment group for the mITT population. Patients for whom a particular therapy name was reported more than once will be counted only once for that therapy.

### 8.3 Protocol Deviation

For all randomized patients, major protocol deviations relating to PPS will be listed. Major protocol deviations, including protocol deviations related to COVID-19, will be specified in the “Protocol deviation plan” separately. A final list of major protocol deviations will be determined based on the data review prior to database lock.

## 9. EFFICACY

Efficacy analyses will be performed for the mITT population unless otherwise specified.

### 9.1 Primary Endpoint

The time from the end of surgery (defined as the time the patient leaves the operating room) to time to first toleration of solid food (defined as the time when the patient consumes a meal that requires chewing and has no significant nausea or vomiting, as per the judgment of the investigator, for 4 hours after that solid food) and first bowel movement (GI2) will be the primary endpoint and called "Time to event of GI2". The time to event of GI2 will be the later time at which all of the following criteria are met:

- First toleration of solid food (as defined above)
- First bowel movement after surgery

If one of three time components (end of surgery time, time when the patient first tolerates solid food, and time of first bowel movement) is missing, time to event of GI2 will be considered as missing.

If time to event of GI2 does not occur during the evaluation period of 240 hours, the patient will be censored at the time of his/her last nonmissing postbaseline assessment.

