5.2 Exclusion Criteria

Patients are excluded from the study if any of the following criteria apply:

Medical Conditions

- 1. Scheduled to undergo a total colectomy or any procedure that results in a colostomy or ileostomy.
- 2. Scheduled for endoscopic or laparoscopic surgery.
- 3. Complete bowel obstruction.
- 4. Complicated inflammatory bowel disease (such as ulcerative colitis or Crohn's disease).
- 5. More than 2 prior major abdominal surgeries (eg, gastrectomy, gastric bypass, gastric sleeve, lap banding, pancreatic resection, hepatectomy, intestinal transplant).

Prior and Concomitant Therapy

- 6. More than 3 doses of an opioid (regardless of the route of administration) during the 7 days prior to surgery.
- 7. Chemotherapy within 4 weeks prior to surgery; otherwise, patients with cancer are eligible.
- 8. Scheduled to receive chemotherapy, immunotherapy, or radiation therapy intraoperatively or within 14 days after surgery; otherwise, patients with cancer are eligible.
- 9. Any prohibited medication within 14 days prior to the first dose of study treatment as specified in [Section 6.5](#).

Prior and Concurrent Clinical Study Experience

- 10. Exposure to an investigational drug within 90 days prior to the start of Screening.
- 11. Prior exposure to naldemedine.

Diagnostic Assessments

12. Severe hepatic impairment.

Other Exclusions

13. Pregnancy or lactation.
14. Presence of peritoneal catheter (eg, for dialysis or chemotherapy).
15. Any other reason considered by the investigator or qualified designee to make the patient ineligible to take part in the study.

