7. DISCONTINUATION OF STUDY TREATMENT AND PATIENT DISCONTINUATION/WITHDRAWAL

7.1 Discontinuation of Study Treatment

A patient may discontinue study treatment prior to Day 10 if he or she meets the primary endpoint, GI2, or on the date on which the discharge order is written, whichever occurs first. Discontinuation of study treatment for any other reason will be determined by the investigator if he or she believes that it is in best interest of the patient. Female patients who become pregnant during the study will be followed as described in [Section 7.2](#), [Section 8.3.5](#), and [Appendix 4](#). The investigator will withdraw a patient from study treatment based on the management and discontinuation criteria for abnormal liver function tests ([Appendix 5](#)). The investigator should consider discontinuation of study treatment if opioid withdrawal is suspected on any assessment day. In addition, discontinuation of study treatment is required if:

- The patient has an unplanned ileostomy or colostomy during the surgical procedure.
- A patient has a score > 36 on the Clinical Opiate Withdrawal Scale (COWS) on any assessment day
- Hypersensitivity thought to be related to study treatment occurs and is considered severe in intensity, as assessed by the investigator
- There is any sign or symptom suggestive of gastrointestinal perforation, as assessed by the investigator

See the SoA for data to be collected at the time of treatment discontinuation (eg, at the Early Termination Visit).

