8.1 Efficacy Assessments

8.1.1 Primary Efficacy Assessments

8.1.1.1 Time from End of Surgery to Time to First Toleration of Solid Food and First Bowel Movement

The time from the end of surgery (defined as the time the patient leaves the operating room) to time to first toleration of solid food (defined as the time when the patient consumes a meal that requires chewing and has no significant nausea or vomiting, as per the judgment of the investigator, for 4 hours after that solid food) and first bowel movement (GI2) will be recorded in the eCRF. First toleration of solid food and first bowel movement will be recorded until the patient meets the primary endpoint described above. If the patient discontinues study treatment, the patient still needs to be followed for GI2 until the achievement of this endpoint or until he/she completes the study. If the patient is withdrawn from the study, first toleration of solid food and first bowel movement, as applicable, will be recorded at the ET Visit (see also [Section 9.4.5.1](#)). If a patient is discharged from the hospital prior to having a first bowel movement, the reason for discharge prior to having the first bowel movement will be recorded in the eCRF. Additionally, the patient will be instructed to inform the investigator or qualified designee by phone, text, or e-mail within 24 hours of having a first bowel movement up to and including Day 10. The investigator or qualified designee will communicate (phone, text, or e-mail) with the patient daily up to and including Day 10 to record when the first bowel movement occurred.

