9.2 Sample Size Determination

The planned sample size of between 44 and 85 patients per treatment in the mITT Population was determined by a simulation study with 10,000 iterations to provide 80% power to demonstrate the linear dose-response relationship between treatment groups (3 naldemedine groups and placebo group) in the primary endpoint at a 2-sided significance level of 0.05. In total, approximately 200 to 340 patients in the study will be required.

The simulation estimated 44 patients per treatment group to see a linear trend in the restricted mean survival time (RMST) up to 240 hours for the time to the event of GI2 across a 24-hour difference between naldemedine 5 mg and placebo under 80% statistical power at a 2-sided significance level of 0.05. Eighty-five patients per treatment group will be required to see a linear trend in RMST up to 240 hours across an 18-hour difference between naldemedine 5 mg and placebo. In addition, the time to the event of GI2 in each group follows the Weibull distribution by referring to the survival curve for the time to the event of GI2 shown in the alvimopan package insert. It was assumed that an independent censoring followed an exponential distribution with a rate such that approximately 20% of patients were censored within 240 hours.

The final sample size will be dependent on the enrollment rate during the fixed enrollment period. A minimum of 44 patients per group in the mITT Population is desired.

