## **5. ANALYSIS POPULATIONS**

### **5.1 Modified Intention-to-treat Population**

The mITT Population will include all randomized patients who received at least 1 dose of study treatment and had at least 1 postbaseline efficacy assessment for the primary efficacy endpoint, which includes all three components (end of surgery time, time when the patient first tolerates solid food, and time of first bowel movement) of the time to event of GI2. Patients will be analyzed according to the treatment to which they were randomized.

This population will be the primary efficacy analysis population.

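### After an unplanned ileostomy or colostomy the plan does not say what counts as a bowel movement, and its rules let the same patient be censored, dropped or counted as an event in the primary analysis

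*SAP*

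**What the plan says.** - **Entry.** Protocol 5.2 excludes patients "Scheduled to undergo a total colectomy or any procedure that results in a colostomy or ileostomy". This covers planned stomas only.
- **Dosing.** Protocol 4.1 gives the first dose before surgery, so a patient whose stoma is decided in theatre is already randomised and treated.
- **Stopping.** Protocol 7.1 requires study treatment to stop if "The patient has an unplanned ileostomy or colostomy during the surgical procedure".
- **Follow-up.** Protocol 8.1.1.1: "If the patient discontinues study treatment, the patient still needs to be followed for GI2 until the achievement of this endpoint", or until study completion. Patients discharged before a bowel movement are contacted daily through Day 10.
- **Endpoint.** In SAP 9.1, GI2 is the later of first tolerated solid food and first postoperative bowel movement. Stoma output is neither counted nor ruled out.
- **Two rules in SAP 9.1.** If any of the three times (end of surgery, solid food, bowel movement) is missing, GI2 is missing. The next rule reads: "If time to event of GI2 does not occur during the evaluation period of 240 hours, the patient will be censored at the time of" the last available postbaseline assessment.
- **Analysis set.** Protocol 9.3 asks for one dose and one postbaseline assessment of the primary endpoint. SAP 5.1 begins the same way ("The mITT Population will include all randomized patients who received at least 1 dose of study treatment") but adds that the assessment includes all three time components.

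No population definition, supplementary analysis or subgroup in either document names these patients.

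**The concern.** The plan foresees this event and regulates treatment after it, but does not carry it through to the endpoint or the analysis set. These patients have had one preoperative dose, and half of their endpoint has no stated meaning. Whether they enter the primary contrast as long event-free times, as early events, or not at all depends on which sentence the programmer follows and on how the site fills in the bowel-movement field.

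The choice matters because the primary test compares RMST to 240 hours in small groups (44 to 85 per arm in the mITT). A few values at the truncation limit can inflate its variance considerably. The SAP statistic also weights the three surgical strata equally, so one patient in a thin stratum-arm can move the estimate.

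**Working it through.** **Inputs from the documents.** Protocol 9.2 sets the test "in the primary endpoint at a 2-sided significance level of 0.05" and the sample size "to provide 80% power to demonstrate the linear dose-response relationship between treatment groups". It gives 44 per group "across a 24-hour difference between naldemedine 5 mg and placebo under 80% statistical power", and 85 per group for 18 hours. Event times are Weibull with about 20% censored by 240 hours. The Weibull parameters are not given. Protocol 9.4.5.1 and SAP 9.1.1 give the contrast (-3, -1, 1, 3).

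**Assumed, not in the documents.** Stoma rate 2%, 5% or 10%, equal in all arms; placebo RMST 90 to 130 h; in the hand calculation, a mean RMST of 110 h in patients without a stoma.

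**Step 1: the plan's own figures.** Without the Weibull parameters, 44 and 85 cannot be reproduced exactly. With equal steps between arms, a difference D gives a contrast of 10D/3 with variance 20·SD²/n, so

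n = 20·SD²·(1.96 + 0.84)² / (10D/3)².

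- D = 24, n = 44: SD = 80·√44 / (2.80·√20) = 42.4 h.
- D = 18, n = 85: SD = 60·√85 / (2.80·√20) = 44.2 h.

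The two figures are consistent. A Weibull simulation calibrated to 80% at n = 44 gave 0.81 at n = 85 for 18 h.

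**Step 2: hand calculation, stoma patients held event-free to 240 h.** With share p and SD 42:

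- difference = 24(1 − p)
- variance = (1 − p)·42² + p(1 − p)·(240 − 110)²
- z = 2.80·(1 − p)·42 / SD_new, and power = Φ(z − 1.96)

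| p | difference (h) | SD (h) | power |
|---|---|---|---|
| 2% | 23.5 | 45.4 | 0.72 |
| 5% | 22.8 | 49.8 | 0.61 |
| 10% | 21.6 | 55.8 | 0.48 |

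Splitting the 5% row: the smaller difference alone gives z = 2.80·0.95 = 2.66, power 0.76. The larger SD alone gives z = 2.80·42/49.8 = 2.36, power 0.66. Most of the loss is variance.

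**Step 3: simulation of each route.** n = 44, 24 h, exponential censoring at 20%, Kaplan-Meier RMST, unstratified contrast. The shape (2.1 to 3.3) was calibrated to about 80% power with no stomas. Ranges are over placebo RMST 90, 110 and 130 h.

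| Handling | 2% | 5% | 10% |
|---|---|---|---|
| No event, followed to 240 h | 0.63–0.69 | 0.47–0.58 | 0.34–0.44 |
| No event, censored at 72–168 h | 0.70–0.78 | 0.56–0.75 | 0.36–0.69 |
| Output counted, placebo-like timing | 0.78–0.79 | 0.74–0.76 | 0.69–0.70 |
| Output counted at 24–72 h in every arm | 0.77–0.79 | 0.71–0.78 | 0.63–0.73 |
| Dropped from the mITT | 0.79–0.80 | 0.76–0.77 | 0.75–0.76 |

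A second simulation (shapes 1.5 to 2.5, placebo RMST 120 to 140 h, n set for 80%) gave 0.74–0.78, 0.64–0.73 and 0.51–0.66 for the first row. At 5% the range for that route is therefore roughly 0.5 to 0.7.

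**Step 4: chance imbalance.** Take five patients in one stratum-arm. One held at 240 h instead of 110 h moves that RMST by 130/5 = 26 h. SAP 9.1.1 averages three strata, so the pairwise difference moves by 26/3 ≈ 8.7 h, against a target of 18 to 24 h and in either direction.

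**The case against.** A reader might infer that these patients stay in the mITT, are given 240 hours, and dilute the contrast. The documents do not support that reading.

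- **Staying in the mITT.** The three-component clause of SAP 5.1, read literally, removes a patient with no bowel-movement time. That reading fits badly with the rest of the plan: it would also drop every other patient who never has a bowel movement, leaving the censoring rule little to act on. But the text is there, and membership is unsettled.
- **240 hours.** No passage assigns it. Censoring is at the last assessment, which approaches 240 h only with follow-up to Day 10. Earlier censoring does not cure the problem, because Kaplan-Meier then treats as non-informative a patient who, on a literal reading, cannot have the event.
- **Dilution.** At 5% the difference falls only from 24 to 22.8 h.
- **Power.** The stoma rate is assumed, and large losses belong to one route. About 50 per group are to be randomised against 44 needed; dropping 5% of 50 leaves 47.5. It also cannot be said that the stated 80% ignores such patients, since the Weibull curve behind it is not shown.

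Exclusion can be challenged too. Protocol 9.4.5.1 continues efficacy evaluation whether or not patients keep taking treatment, and a stoma is a post-randomisation, post-dose event. That is a fair objection, and it is why counts by arm and an inclusive analysis are needed. The Protocol Deviation Plan, which is not among the documents, may remove these patients from the Per-protocol Set, but that set is supplementary and would not settle the primary analysis.

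**Conclusion.** The gap is real and should be closed before unblinding. For one foreseeable type of patient, the endpoint component is undefined and the documents allow three results: censored, dropped or missing, or an event. The size depends on the handling and on an unstated rate. At an assumed 5% in every arm (0.05 × 44 = 2.2 patients per arm) and nominal 80% power, it is roughly 0.5 to 0.7 if patients are held event-free to 240 h. It is roughly 0.74 to 0.77 if they are dropped or output counts with placebo-like timing, and 0.71 to 0.78 if output counts at 24 to 72 h. The simulations use an unstratified contrast and assumed placebo RMSTs, so the ranking of the routes is firmer than any single figure. With equal rates the main harm is loss of precision; unequal numbers by chance could bias the contrast either way.

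**What to change.** Before unblinding, in the SAP:

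1. Reconcile the three-component clause of SAP 5.1 with the missing-component and censoring rules of SAP 9.1, so that patients who do not reach GI2 are censored and not dropped.
2. State in SAP 5.1 that patients in whom an ileostomy or colostomy was created at the index operation are excluded from the primary mITT. Fix that status under blind from the operative record, and report the number by arm.
3. Add a supplementary analysis that includes them under a stated coding of stoma output, for example once as the bowel-movement component and once as no event.
4. Keep them in the Safety Population.

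The cost is SAP wording, a blinded check of operative records and the extra supplementary runs. The downside is that a few randomised and dosed patients leave the primary set, for an intraoperative reason that is plausibly, but not provably, independent of arm.

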BID = twice daily; COWS = Clinical Opiate Withdrawal Scale; eCRF = electronic case report form; EDC = electronic data capture; IV = intravenous; IWRS = Interactive Web Response System; NPRS = Numerical Pain Rating Scale; PK = pharmacokinetics

- a To be recorded in the eCRF through the End-of-study Visit, which will occur 30 days after Day 10 or after the day of discharge (whichever is sooner), with a window of + 3 days, but not < 30 days. Patients will receive no more than a total of 11 days of study treatment (Day 0 [day of surgery] plus up to 10 days beginning on Day 1).
- b These assessments will be performed for patients who discontinue study treatment and for those who are withdrawn from the study.
- c The End-of-study Visit will occur 30 days after Day 10 or after the day of discharge (whichever is sooner), with a window of + 3 days, but not < 30 days (preferably in person, but by phone if necessary).
- d Includes prior and current conditions and all past surgeries; to be recorded on eCRF.
- e Includes (as applicable to the study period) a review of prior and current therapies. The preoperative bowel preparation, if any, as well as the total volume of IV fluids administered during surgery, must be recorded in the eCRF. Intra-operative and postoperative opioid analgesics administered to patients will be recorded in the eCRF.
- f Time of the beginning of surgery is defined as the time when the first incision is made. Time of end of surgery is defined as the time the patient leaves the operating room.
- g The 3 enhanced recovery protocol elements required by the protocol (early removal of the nasogastric tube [defined as removal of the nasogastric tube at end of surgery], early ambulation [defined as ambulation on Day 1], early diet advancement on Day 1) and 4 other elements at the study site (antibiotic prophylaxis, preoperative carbohydrate drink, epidural anesthesia in addition to general anesthesia, and chewing gum postoperatively) must be recorded as yes or no in the eCRF at Baseline (planned) and at the day of discharge or early termination (actual).
- h A preoperative physical examination within 2 weeks prior to the patient signing the informed consent form may be used, as long as the eCRF is completed.
- i As per standard of care at the hospital or, for End-of-study Visit, at the hospital or doctor's office.

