9.4.5.1 Primary Efficacy Endpoint

The primary endpoint will be time from the end of surgery (defined as the time the patient leaves the operating room) to time to first toleration of solid food (defined as the time when the patient consumes a meal that requires chewing and has no significant nausea or vomiting, as per the judgment of the investigator, for 4 hours after that solid food) and first bowel movement (GI2).

The mean survival time, which is also referred to as the RMST, of GI2 events within 240 hours will be estimated using the area under the Kaplan-Meier (KM) curve. To demonstrate the linear dose-response relationship between treatment groups (3 naldemedine groups and placebo group) and the RMST, the linear contrast test for trend with contrast coefficients of (-3, -1, 1, 3) will be performed. If a dose-response relationship is detected, then pairwise comparisons of the RMST between each dose group of naldemedine and the placebo group will be conducted, and the treatment differences (with its 95% confidence interval [CI]) will be provided. If an event does not occur during the evaluation period of 240 hours, the patient will be censored at the time of his/her last nonmissing postbaseline assessment. The same analysis will be performed in the Per Protocol set. In addition, the reason for discharge prior to having the first bowel movement will be listed.

Patients will continue to be evaluated for efficacy regardless of treatment adherence. The use of additional therapies or interventions that could treat any component of the primary endpoint (eg, motility agents, anti-emetics, laxatives, etc), may confound the results of the primary efficacy analysis. This list of therapies will be finalized before database lock. To examine this issue, the following exploratory analyses of the GI2 endpoint will be performed or provided:

- Repeat of the primary analysis, excluding all patients who received additional therapies at any time postrandomization that could treat any of the components of the GI2 endpoint. It is recognized that this subset is selected based on postrandomization decisions, may be confounded with the treatment group, and may not represent a randomized subgroup of the primary endpoint.
- Table of proportion of patients in each treatment group who received additional therapies that could treat any of the GI2 components.

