## 6.4 Missing Data

Missing values will not be imputed. All statistical analyses will be based on observed cases unless otherwise noted.

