## 13.2 Sample SAS Code

When dataset A has time of GI2 and censored information, there are mainly 3 steps to calculate RMST.

(1) GI2 after 240 hours should be censored before calculating RMST until 240 hours.

```
DATA B;  
SET A;  
  IF (hour > 240) then status=0;  
RUN;
```

(2) The program below will provide  $\hat{\mu}_{kg}(t)$  in the dataset C0. The number of GI2 (saved in a variable ‘Failed’) will be given in the dataset C1, where hour is GI2 time, status=0 if censored, 1 if not censored, surgery is surgery procedure, treatment is treatment group.

```
ODS OUTPUT MEANS=C0 CENSOREDSUMMARY=C1;  
PROC LIFETEST DATA=B TIMELIM=240;  
  BY surgery;  
  TIME hour*status (0);  
  TEST treatment;  
RUN;
```

(3) Standard deviation of each RMST  $\sqrt{Var[\hat{\mu}_{kg}(t)]}$  will be given as ‘sd’. The test statistics T and S defined in section 9.1.1 will be calculated by these estimates of RMST and SDs.

[figure not shown]
```
DATA D;  
MERGE C0(IN = A) C1;  
BY treatment surgery;  
sd = StdErr *SQRT((Failed – 1)/Failed);  
IF A;  
RUN;
```

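### The primary censoring time is neither tied to GI2 status nor capped at 240 h, so a patient whose GI2 was not ascertained can be carried to 240 h, censored earlier or dropped

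*SAP*

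**What the plan says.** SAP 9.1 says of a patient without GI2 in the 240-hour evaluation period that "the patient will be censored at the time of his/her last nonmissing postbaseline assessment". Protocol 9.4.5.1 has the same sentence. Neither says which assessment is meant.

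Three other SAP sentences bear on the same patient:

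- Just above the censoring sentence, SAP 9.1 says that if the end-of-surgery, solid-food or bowel-movement time is missing, "time to event of GI2 will be considered as missing".
- SAP 6.4: "Missing values will not be imputed".
- SAP 5.1 admits to the mITT Population patients who "had at least 1 postbaseline efficacy assessment for the primary efficacy endpoint, which includes all three components".

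The SAS step in SAP 13.2, "IF (hour > 240) then status=0", changes the status of a late time but not the time itself.

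The End-of-study Visit (Protocol 1.3, SoA footnote c) falls at least 30 days after Day 10 or discharge. For patients discharged before a first bowel movement, Protocol 8.1.1.1 asks for daily contact up to Day 10. Protocol 9.2 assumes independent exponential censoring, with about 20% of patients censored within 240 hours.

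**The concern.** A Kaplan-Meier censoring time should be the last time the patient was known to be event-free. The mITT definition limits its assessment to one for the primary endpoint; the censoring sentence carries no such limit. A programmer who follows it literally takes the latest postbaseline record.

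That record will often lie beyond 240 h. Protocol 8.3.1 collects adverse events up to the End-of-study Visit, the SoA records readmission then, and Protocol 7.2 asks patients to stay in the study until that visit even when off treatment. A missed End-of-study Visit triggers repeated contact attempts (Protocol 7.3). No such retry rule is stated for the daily GI2 contacts.

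Take a patient discharged on Day 3 without a bowel movement, not reached by the daily contacts, but seen at the End-of-study Visit. The literal rule counts this patient as unrecovered for all 240 h, although nothing is known after Day 3. That raises RMST and its variance, and biases the comparison if arms differ in the share affected.

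**Working it through.** **Step 1. Where one patient can end up.** The End-of-study Visit is at least 30 × 24 = 720 h after discharge or Day 10, so always beyond 240 h. If it sets the censoring time, the SAS step marks the patient as censored but leaves the time above 240, and the patient stays at risk to the horizon. The texts therefore allow three outcomes for a patient with unascertained GI2:

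- (a) censored at the last GI2 contact, if the assessment means a GI2 assessment;
- (b) carried to 240 h, if any record counts;
- (c) dropped, if the missing-component, no-imputation and mITT sentences govern.

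**Step 2. The plan's sample sizes.** With a linear trend and difference D between the extreme groups, the contrast (−3, −1, 1, 3) equals −10D/3 and has variance 20σ²/n. For 80% power at two-sided 0.05:

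n = 20σ²(1.960 + 0.842)² / (10D/3)² ≈ 14.13σ²/D²

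- n = 44, D = 24 h gives σ = 42.4 h.
- n = 85, D = 18 h gives σ = 44.2 h.

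The Weibull parameters are not in the documents, so 44 cannot be derived from scratch. I assumed a placebo RMST of 90, 110 or 130 h and calibrated the shape to n = 44 at 24 h. The 18 h case then needs 82–84 per group against 85 stated, so the two figures are mutually consistent.

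**Step 3. Bias under (b).** Each unascertained patient contributes 240 h in place of about the arm's RMST, so bias per arm ≈ f × (240 − RMST). At RMST 110 h:

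- f = 5%: 0.05 × 130 = 6.5 h
- f = 10%: 0.10 × 130 = 13 h
- f = 20%: 0.20 × 130 = 26 h, more than the 24 h target difference

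**Step 4. Power.** I simulated the unstratified contrast on KM-RMST to 240 h (3,000 to 4,000 runs per scenario) with one censoring rate common to all arms. The 20% in Protocol 9.2 can be read in two ways. One is that the censoring time falls below 240 h with probability 20%, so that about 7–11% are actually lost before GI2. The other is that 20% are actually lost before GI2. Ranges are over the three assumed placebo RMSTs.

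| Handling | 44 per group, 24 h: P(C<240) = 20% | 44 per group, 24 h: 20% lost | 85 per group, 18 h: P(C<240) = 20% | 85 per group, 18 h: 20% lost |
|---|---|---|---|---|
| (a) Last GI2 status | 81–82% | 79–81% | 81% | 81–82% |
| (b) All carried to 240 h | 57–59% | 43–48% | 59–60% | 46–51% |
| (c) Dropped | 77–78% | 73–75% | 78–79% | 72–76% |

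Under (a) RMST is unbiased. Under (b) it rises by about 10–11 h on the first reading and 21–30 h on the second. Under (c) it falls by about 1–2 h and 2–5 h. With a common censoring rate the arm difference under (b) is roughly kept (100.1 − 75.3 = 24.8 h in the first case run), so the lost power comes mainly from added variance.

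**Step 5. Unequal loss, no drug effect.** These shares are hypothetical. With RMST 110 h, and loss falling from 15% on placebo to 5% on 5 mg, handling (b) gives a false benefit of about 0.10 × 130 = 13 h. The two-sided rejection rate is 21% at 44 per group and 34% at 85, against 5–6% under (a). With equal 5% loss it stays near 5.5%.

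**The case against.** A reader might infer that the plan censors at the last assessment of any kind, so that every unascertained outcome becomes the worst outcome and the 80% power claim fails. The documents do not support that:

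- They never say that any assessment counts. The sentence stands under the primary endpoint, where an assessment of that endpoint is a natural reading.
- Protocol 9.2 expects about 20% censored within 240 h. If End-of-study records counted, nobody attending that visit could be censored earlier, so the sample-size text points to GI2-based censoring.
- The missing-component, no-imputation and mITT sentences could exclude the example patient instead, at a smaller cost in power (outcome (c)).
- Daily contact to Day 10 covers roughly the whole 240 h window. Patients who stop treatment are still followed for GI2, and withdrawn patients have it recorded at the Early Termination Visit. A patient confirmed without GI2 through 240 h is correctly at risk throughout.

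All of this stands. It limits the exposed group to patients whose contact lapsed or whose component time is missing. It does not settle which handling applies to them, and the literal text together with the sample code still permits (b). A patient who recovered but whose time was not recorded is also exposed. After discharge, Protocol 8.1.1.1 describes capture of the bowel movement only, not of solid-food toleration.

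**Conclusion.** The concern holds as an undefined censoring time in the primary analysis. Its literal reading gives a wrong RMST, and the surrounding text allows two other treatments of the same patient. The choice should not be left to programming.

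The bias formula needs only f and RMST, and assumes that unascertained patients would otherwise have had about the arm's mean time. The power figures rest on the assumed Weibull range, a common censoring rate, an unstratified contrast, and every unascertained patient attending the End-of-study Visit. The drop to 57–60% or 43–51% is therefore the full-carry case. The actual share is not given, so these are not predictions. Equal loss across arms costs power without noticeably inflating type I error; only unequal loss creates a false difference, and the documents neither establish nor rule that out.

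**What to change.** In SAP 9.1 and Protocol 9.4.5.1, write: *A patient without GI2 by 240 hours is censored at the earlier of 240 hours and the last time GI2 was known to be unmet, from an in-hospital assessment or a post-discharge contact. Safety and End-of-study records do not extend this time. A patient confirmed without GI2 through 240 hours is censored at 240 hours.*

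Also:

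- Reconcile the missing-component sentence (SAP 9.1) and the three-component mITT text (SAP 5.1), so that such patients are censored, not excluded.
- Confirm that dates of negative daily contacts are captured in the eCRF. The documents describe recording when the bowel movement occurred, not contacts at which it had not.
- For the discharge endpoints that borrow this censoring (SAP 9.2.1, 9.3.1, 9.3.2), censor at the earlier of 240 h and the last time the patient was known not to have had that endpoint's own event. A GI2-based cutoff would be wrong there. GI2 assessment stops once GI2 is met, so an inpatient with GI2 at 60 h and no discharge order by 240 h would be censored near 60 h.

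The cost is a few sentences and a revised derivation before database lock, plus an eCRF field if negative contacts are not yet recorded.
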